5.10. Health Outcomes Assessments

The CHAQ and HAQ will be summarized in the same way as the efficacy endpoints. CHAQ and HAQ results will be summarized separately.

5.11. Exposure

The exposure time (years) to etanercept will be calculated for each subject each period using (the last dose date – the first dose date + 1)/365.25. If the gap is less than 28 days between two etanercept treatment periods, the cumulative exposure will include the gap. Otherwise, the gap will be excluded from the cumulative exposure. Descriptive statistics will be provided to summarize the exposure time for:

- FAS, on-drug period (active and re-treatment periods together);
- FAS, all periods (includes commercial etanercept in withdrawal and observational periods).

The total number of doses of investigational product taken will be summarized for FAS (active and re-treatment periods together).

A table showing the number of subjects taking investigational product for 1 year, 2 years and so on through 10 years may be provided for FAS (active and re-treatment periods together).

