8.2. Reporting Period

For SAEs, the active reporting period to Pfizer or its designated representative begins from the time the subject provides informed consent, which is obtained prior to the subject’s participation in the study, ie, prior to undergoing any study-related procedure and/or

receiving investigational product, through at least 96 months after the baseline visit in study B1801023. In addition, for subjects who are either in the active treatment period or the re-treatment period at Month 96, serious adverse events will be collected until 30 days after the last dose of investigational product. SAEs occurring to a subject after the active reporting period has ended should be reported to the Sponsor if the investigator becomes aware of them; at a minimum, all SAEs that the investigator believes have at least a reasonable possibility of being related to investigational product are to be reported to the Sponsor.

AEs (serious and nonserious) should be recorded on the CRF from the time the subject enters either the active treatment period or withdrawal/re-treatment period at the baseline visit of study B1801023 through the subject's last visit in the active treatment period and/or the withdrawal/re-treatment period of the study and for 30 days after the last dose of investigational product for those subjects who are in either the active treatment period or the re-treatment period at Month 96.

For subjects in the active treatment period:

All adverse events (serious and non-serious), including infections, medically important infections, injection site reactions, and malignancy must be recorded on the CRF from the time the informed consent is signed through the Month 96 visit or upon early withdrawal from the study. All adverse events will be collected for the duration of the active treatment period and for 30 days after the last dose of investigational product for those subjects who are either in the active treatment period or the re-treatment period at Month 96.

Events reported as ongoing at the final study 0881A1-3338 visit as well as events starting between the final study 0881A1-3338 visit and baseline visit of study B1801023 must also be recorded on the appropriate CRF.

For subjects in the withdrawal/re-treatment period:

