4.2.2. Secondary Endpoints

The secondary endpoints include

- *the occurrence of serious adverse events (SAE, infectious and non-infectious events will be summarized separately),*
- *the occurrence of medically important infections (ie, an infection requiring hospitalization and /or parenteral [intravenous (IV), intra-muscular (IM)] anti-infective agents).*
- Hospitalization: For any hospitalizations, the admission date, discharge date and reason for hospitalization will be collected during the study.
- Death: For any deaths, date of death and cause of death will be collected during the study.

- Nonstudy medication: nonstudy medications are coded using the WHO Drug Dictionary (2006 Q3). The Prior, Concomitant, After (PCA) flag for nonstudy medications will be derived for both parent study and extension study (only for active treatment period):
 - Prior nonstudy medications are defined as any nonstudy medications taken before the first dose of investigational product taken at the start of the study,
 - Concomitant nonstudy medications are defined as any nonstudy medications taken during the treatment period (from the first dose to the last dose of the investigational product).
 - After nonstudy medications refer to any nonstudy medications taken after the last dose of the investigational product.(not applicable for observational period)
- Exposure: the total number of doses taken and exposure time.

The above endpoints will be collected for all subjects. The following endpoints will be collected only for subjects in the active treatment period, or withdrawal/re-treatment period in the extension study:

Non-serious adverse Events (Adverse events that occur up to 30 days after the last dose of investigational product will be counted as having occurred during the treatment period) This is applied for active and retreatment periods. If an AE started in active or retreatment period and continued into withdrawal or observational period, it will be only counted in active or retreatment period, it will not be counted in withdrawal or observational period again. If an event started in withdrawal or observational period, and after 30 days of the last dose of investigational product of active period or re-treatment period, this event will not be counted.

Occurrence of withdrawals from investigational product due to adverse events;

Laboratory evaluations (ie, hematology, blood chemistry, and CRP)

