5.2. Treatment-emergent Events

An event is defined as a treatment-emergent event if the event occurred during the active period (either parent or extension studies) or re-treatment period with onset dates between the first dose date of investigational product and within 30 days after the last dose of investigational product. If a treatment-emergent event started in active or re-treatment period and continued to withdrawal or observational period, it will be only counted in active or re-treatment period, it will not be counted in withdrawal or observational period again. If an event started in the withdrawal or observational periods, and after 30 days of the last dose of investigational product of the active period or re-treatment period, this event is not a treatment-emergent event.

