5.5. Malignancies, SAE and Medically Important Infections

The malignancies, serious adverse events and medically important infections will be summarized using the frequency and percentage of subjects reporting events. The adjusted rate per 100 subject-years of exposure to etanercept (defined as # of events/total exposure*100) will be summarized also.

The incidence of malignancies may be compared to external data sources to generate standardized incidence ratios (SIRs) to aid interpretation.

In addition to showing cumulative rates over the entire study period (including both parent study and extension), incidences of subjects with malignancies, serious adverse events and medically important infections as well as exposure-adjusted rates will also be categorized by year for each year from 1 through 10.

These summaries and analyses will be performed for:

- FAS, all events in all periods;
- FAS, treatment-emergent events in the on-drug period (active and retreatment periods together).

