5.6. General Adverse Events

The occurrence of all treatment-emergent adverse events (excluding infection and ISR), infections, infections considered preventable by vaccination, and injection site reactions will be separately summarized by incidence rate (proportion of subjects reporting events) and adjusted rate per 100 subject-years of exposure to etanercept. Adverse events will also be summarized by severity and relationship to investigational product. Adverse events occurring in >1 subject in any of the subtypes may be summarized as well.

- Tabulations of withdrawals from investigational product due to adverse events will be provided.
- In addition to showing cumulative rates over the entire study period (including both parent study and extension), incidences of subjects with treatment-emergent event as well as exposure-adjusted event rates will also be categorized by year for each year from 1 through 10.

These summaries will be performed for FAS (treatment-emergent events in on-drug period (active and retreatment periods together)) and WAS.

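### The exposure-adjusted on-drug rates count events up to 30 days after the last dose, but their denominator stops at the last dose, which biases them upward: about 1–2% cumulatively, more in Year 10

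*SAP*

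**What the plan says.** **Numerator.** SAP 5.2 counts an event as treatment-emergent if it falls in the re-treatment period, or in the active period of either study, "with onset dates between the first dose date of investigational product and within 30 days after the last dose of investigational product". SAP 4.2.2 gives the same window for events that are non-serious: "Adverse events that occur up to 30 days after the last dose of investigational product will be counted as having occurred during the treatment period".

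**Denominator.** Under SAP 5.11, exposure "will be calculated for each subject each period using (the last dose date – the first dose date + 1)/365.25". Only one thing lengthens it: "If the gap is less than 28 days between two etanercept treatment periods, the cumulative exposure will include the gap". That rule bridges two treatment periods. It adds nothing after a final dose.

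**Rate.** SAP 5.5 gives the adjusted rate for malignancies, serious adverse events and medically important infections as "defined as # of events/total exposure*100". One of its two analyses is restricted to treatment-emergent events in the active and re-treatment periods together. SAP 5.6 reports the other treatment-emergent events as an "adjusted rate per 100 subject-years of exposure to etanercept". Both sections plan a cumulative figure over the two studies and one for each of Years 1 to 10.

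**The concern.** In a rate per person-time, events and time should come from the same window. Here every end of treatment opens up to 30 days in which an event can be counted but no person-time accrues. The error runs one way: a rate is either correct or too high. A subject who stops, withdraws and is re-treated contributes two such tails.

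The pattern over time also matters. Nearly everyone still on drug stops in the last year, so the bias concentrates there. A rise in Year 10 could be read as an effect of long exposure when part of it comes from how the rate is built. SAP 5.5 also allows malignancy incidence to be compared with external sources, where matched events and person-time are needed.

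**Working it through.** The plan states no figure for these rates or their bias, so there is nothing to reproduce. The check is person-time arithmetic.

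**Inputs from the documents**
- Tail counted in the numerator: 30 days (SAP 5.2).
- Parent-study treatment: 96 weeks = 96 × 7 = 672 days (SAP 1).
- Extension treatment: up to 96 months = 8 × 365.25 = 2,922 days (SAP 2.2.1).
- Gap between the last parent dose and the first extension dose: up to 6 weeks (Protocol 4.1.2).
- Month 96 visit window: ±14 days (Protocol 6.1.1.2).

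**Assumptions**
- The event hazard is the same in the tail as on drug. The documents give no event rates.
- Years run from the first parent-study dose. The SAP text does not define the years, and SAP 5.1 leaves analysis intervals to a separate specification.
- Stopping rates of 0.05, 0.10 and 0.20 per year are illustrative.

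**Formula.** Relative inflation = tail days counted in the interval ÷ exposure days in the interval.

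**Cumulative rate, treated to Month 96.** Exposure is 672 + 2,922 = 3,594 days (9.84 years). Inflation is 30/3,594 = 0.83%. With two tails and the same exposure it is 60/3,594 = 1.7%.

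**Cumulative rate with stopping.** At a constant stopping rate *h* per year, mean exposure is (1 − exp(−9.84*h*))/*h* years, and the tail is 30/365.25 = 0.0821 year.

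| *h* per year | Mean exposure (years) | Cumulative inflation | Each of Years 1–9 (about 0.0821 × *h*) | Year 10 (simulated) |
|---|---|---|---|---|
| 0.05 | 7.77 | 1.1% | 0.4% | 10.0% |
| 0.10 | 6.26 | 1.3% | 0.8% | 10.2% |
| 0.20 | 4.30 | 1.9% | 1.6–1.7% | 10.7% |

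A year in which nobody stops has no inflation, apart from any tail that spills over from a stop in the last 30 days of the year before.

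**Year 10.** A subject treated to Month 96 has 3,594 − 9 × 365.25 = 306.75 dosing days in Year 10, and 30/306.75 = 9.8%.

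**Sensitivity of the Year 10 figure**
- Included gap of 0–27 days, Month 96 visit ±14 days, last dose 0–7 days before the visit: about 9.0% to 10.5% in most combinations.
- A 27-day gap with a +14-day visit pushes part of the tail past Year 10. With the last dose at the visit, 17.5/347.75 = 5.0%; with the last dose 7 days earlier, 24.5/340.75 = 7.2%.
- Gap of 28 to 42 days, which 5.11 excludes from exposure: 30/334.75 = 9.0% down to 16.5/348.75 = 4.7%.
- Year 10 read as extension Months 84–96: 30/365.25 = 8.2%.

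**After matching the windows.** For a Month 96 completer the Year 10 denominator rises from 306.75 to 336.75 days, so the rate falls by 30/336.75 = 8.9%. The cumulative denominator rises from 3,594 to 3,624 days.

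**The case against.** The strongest reply is that this hardly matters. About 100 subjects are expected, so Year 10 holds at most about 100 × 306.75/365.25 = 84 subject-years. One event there has an exact 95% Poisson interval of 0.03 to 5.6 events. Ten events over the whole study have an interval of 4.8 to 18.4, which is −52% to +84%, against a bias of 1–2%. The analysis is descriptive, and the available text sets no test or threshold on these rates. All of this stands, and it is why the point is minor. It does not make the two windows agree.

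A second reply is that Protocol 9.4.2 itself asks for rates per subject-year of exposure to etanercept, and the 30 days are off drug. That is fair, and it affects the labelling of the fix.

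Three stronger readings are tempting, and the documents do not support them.
- *Every on-drug safety figure is inflated, by about 10%.* SAP 5.5 and 5.6 also report numbers and proportions of subjects, which use no person-time. The 10% belongs to Year 10 only, under one definition of the year.
- *The primary malignancy result is materially biased.* The primary endpoint covers all subjects, and the first analysis in SAP 5.5 takes all events in all periods, so the 30-day window does not define its numerator. The comparison with external data is optional, and the SAP does not say that it would use the on-drug rate.
- *Events that continue from the parent study into the extension are counted twice.* Protocol 8.2 requires that "Events reported as ongoing at the final study 0881A1-3338 visit as well as events starting between the final study 0881A1-3338 visit and baseline visit" be recorded in the extension, but that is a rule for the case report form. SAP 5.2 classifies events by onset date across both studies, so a re-recorded event keeps its parent-study onset. Nothing shows that double counting is planned.

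**Conclusion.** The mismatch is in the text: the treatment-emergent window runs 30 days longer than the exposure that divides it, for each treatment stint. The exposure-adjusted on-drug rates in SAP 5.5 and 5.6 are therefore biased upward in expectation. Cumulatively the bias is below 1% for full completers and 1–2% under the stopping rates tried. In Year 10 it is about 10%, with a range of roughly 5–11% depending on how the year, gaps, visit timing and stopping fall.

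The sizes rest on equal hazard in the tail. For the non-serious events in SAP 5.6 they are upper figures before Month 96, because Protocol 8.2 does not collect such events once a subject has moved to the observational period, so part of that tail goes unobserved.

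The body of Protocol 9.4.1 and the SAP text just ahead of Section 3.2 were not available to me. A reconciling rule there cannot be excluded, although 5.11, which defines exposure, contains none. This is a worthwhile clarification, not a threat to the study's conclusions.

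**What to change.** For treatment-emergent rates, define time at risk per treatment stint as last dose − first dose + 1 + 30 days. Truncate it at restart of investigational product, death or end of follow-up, where end of follow-up means the end of collection for the type of event being counted. Split it by year in the same way as the events, and state in the SAP when each of Years 1 to 10 begins.

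Label the denominator as treatment-emergent time at risk, and note in the SAP that this departs from the wording of Protocol 9.4.2. Keep the 5.11 exposure for the dosing summaries.

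The cost is a few lines of SAP text and one derived variable. No new data or visits are needed, and the rates become slightly lower. Ending the numerator at the last dose would also match the windows, but it would discard the 30-day rule that SAP 5.2 and 4.2.2 both adopt.

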5.12. Nonstudy Medications

The number (%) of subjects using nonstudy medications will be reported by medication type (DMARD, NSAID, etc) for FAS (on-drug period (active and re-treatment periods together)) and WAS.

Separate tabulations will be provided for prior to, concomitant with or after investigational product will be provided for FAS (on-drug period (active and re-treatment periods together)).

5.13. Hospitalizations

Listings of subjects who are hospitalized will be provided for FAS.

5.14. Deaths

Listings of any deaths that occur will be provided for FAS.

The incidence of death may be compared to external data sources to generate standardized incidence ratios (SIRs) for:

- FAS, all periods;
- FAS, on-drug period (active and re-treatment periods together).

5.15. Data Monitoring Committee

This study will use an Internal Review Committee (IRC) to help assess the safety of the study. The IRC will be responsible for evaluation of periodic assessments of safety and efficacy data. A separate Charter will describe and govern the IRC's activity.

5.16. Data Derivation and Missing Data Handling

The following rules will be used to derive the endpoints and handle the missing components. If an endpoint is missing after derivation, the missing value will not be imputed.

5.16.1. Number of Active Joints

The active joints are defined as joints that are swollen or, in the absence of swelling, joints with limited range of motion accompanied by pain and/or tenderness. Total number of active joints is the number of active joints prorated for missing joints. It is defined as $73 * (\text{total number of active joints with score greater than zero}) / \text{number of non-missing active joints}$. Joint replacement (JR) and not evaluable (NE) are treated as missing. If more than 36 active joint scores are missing, then the total number of active joints will be defined as missing.

5.16.2. Number of Joints with Limited Range of Motion

Total number of joints with limited range of motion is the number of joints with limited range of motion prorated for missing limited range of motions. It is defined as $69 * (\text{total number of joints with score of limited range of motion greater than zero}) / \text{number of non-missing limited range of motions}$. Joint replacement (JR) and not evaluable (NE) are treated as missing. If more than 34 scores of limited range of motion are missing, then the total number of joints with limited range of motion will be defined as missing.

5.16.3. CHAQ/HAQ

For subjects < 18 years of age, the CHAQ will be used and completed by the subject's parent or legal representative/guardian. For subjects \geq 18 years of age, the HAQ will be used and completed by the subject. CHAQ/HAQ contains eight domains: dressing, arising, eating, walking, hygiene, reach, grip, and common activities. Each item within a domain is scored on a 4-point Likert scale from 0 to 3: 0=no difficulty; 1=some difficulty; 2=much difficulty; 3=unable to do. Not applicable is defined as missing. The highest score reported for a domain determines the score for that domain. In addition, a series of questions about use of aids or devices or help (e.g a cane for walking) are asked for each subscales. If the subscale score, based on the ordinal response, is missing, 0 or 1, but at least one of the aids or devices or help is used, the score is set to 2. The overall CHAQ/HAQ is computed as the sum of domain scores and divided by the number of domains answered. If 3 or more domains are missing, CHAQ/HAQ is defined as missing.

5.16.4. ACR Pedi Response

Scoring algorithm including missing data handling for ACR Pedi 30, 50, 70, 90, and 100: First, if any of the components have a score of zero at baseline and the post baseline score is >0, that component will be treated as worsening >30% for scoring improvement; if the baseline score is 0 and the post baseline score is also zero, improvement will be set to 0%. Then the algorithm described in the table below will be applied, based on the number of components with worsening >30%, missing, and improvement >30% (or 50% for ACR Pedi 50, etc).

Worsening>=30%	Missing	Improvement>30%	Outcome
>=2			Non-responder
1	0	>=3	Responder
		<3	Non-responder
	1	>=2	Missing
		<2	Non-responder
	2	>=1	Missing
		0	Non-responder
>=3			Missing
0	0	>=3	Responder
		<3	Non-responder
	1	>=3	Responder
		2	Missing
	>=2	<2	Non-responder

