7.3. Efficacy Assessments

For subjects in the active treatment period, and in the withdrawal/re-treatment period, efficacy will be assessed.

1. The following assessments will be completed by the subject's parent or legal representative/guardian for subjects aged <18 years; these will be completed directly by subjects aged ≥18 years at the time of the assessment.
 - Patient/Parent Global Assessment: The subject or parent will assess all the ways that arthritis affects the subject using a scale between 0 and 10 on a 21-circle VAS with 0 = Very Well and 10 = Very Poor. This is to be completed in a manner that does not bias the investigator's assessment of the subject.

- Pain Assessment: The subject or parent will assess how much pain the subject has had because of his/her illness in the past week (0-10 on a 21-circle VAS with 0= no pain and 10=very severe pain). The Pain Assessment should be completed before the joint assessment.
 - Duration of morning stiffness: Based on the investigator questioning the subject or parent, the time elapsed when the subject awoke in the morning and was able to resume normal activities without stiffness will be provided in minutes and cannot exceed 1440 minutes within 24 hours; If morning stiffness was continuing at the time of assessment or was unusual compared to the recent past, the average duration of stiffness over the past 3 days should be reported.
 - Overall Back Pain and Nocturnal Back Pain ([0-100 mm VAS with 0= no pain and 100= most severe pain], ERA subjects only).
2. PGA of Disease Activity: The investigator will estimate the subject's overall disease activity for the current day by using a scale between 0 and 10 on a 21-circle VAS with 0 = No Activity and 10 = Maximum Activity. This is to be completed in a manner that does not bias the Patient/Parent Global Assessment
 3. Number of active joints, defined as joints with swelling or, in the absence of swelling, joints with limitation of motion with pain and /or tenderness. Joint assessors will assess 68 joints for swelling, 69 joints for limitation of motion, and 75 joints for pain and/or tenderness on motions as follows: 0=no swelling, limitation of motion, or pain and/or tenderness on motion; 1=any swelling, limitation of motion, or pain and/or tenderness on motion; JR = joint replacement; NE=not evaluable

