Tanner Stage Assessment for subjects <18 years of age or who have a score of <5 on 1 or more applicable domain(s). The Tanner Assessment does not need to be repeated if it was performed within 2 months before the early withdrawal visit.

Vital Signs: Temperature, blood pressure (mmHg) and pulse rate (beats/min, after sitting for at least 5 minutes);

Growth parameters: height, weight, BMI;

- Efficacy:
 - *ACR Pediatric 30, 50, 70, 90, and 100, defined as $\geq 30\%$ (and 50%, 70%, 90%, 100%, respectively) improvement from baseline in at least 3 of the 6 following variables, with no more than 1 of the remaining variables worsening by $> 30\%$:*
 - *Physician's Global Assessment (PGA) of Disease Activity on a 21-circle visual analogue scale (VAS);*
 - *Patient/Parent Global Assessment on a 21-circle VAS;*
 - *Childhood Health Assessment Questionnaire (CHAQ)*

- *Number of joints with active arthritis, defined as joints that are swollen or, in the absence of swelling, joints with limited range of motion accompanied by pain and/or tenderness;*
- *Number of joints with limited range of motion;*
- *Laboratory measure of inflammation, c-reactive protein (CRP);*

(Note: ACRPedi responses will be calculated based on parent study baseline. For subjects aged ≥ 18 years, CHAQ is missing)

- *Individual components of the ACR Pediatric Assessments;*
- *Pain Assessment on a 21-circle VAS;*
- *Duration of morning stiffness in minutes;*
- *Clinically inactive disease defined as follows per 2011 Wallace Criteria:*
 - *No joints with active arthritis (defined as joints that are swollen or, in the absence of swelling, joints with limited range of motion accompanied by pain and/or tenderness);*
 - *No fever, rash, serositis, splenomegaly, or generalized lymphadenopathy attributable to JIA;*
 - *No active uveitis;*
 - *CRP level within normal limits in the laboratory where tested or, if elevated, not attributable to JIA;*
 - *PGA of disease activity score of best possible on the scale used;*
 - *Duration of morning stiffness of ≤ 15 minutes;*
- *The Juvenile Arthritis Disease Activity Score (JADAS), using 4 components (PGA of Disease Activity, Patient/Parent Global Assessment, number of joints with active arthritis and CRP).*

- *Additional Secondary Endpoints for ERA Subjects*
 - *Overall Back Pain and Nocturnal Back Pain on a 100 mm VAS;*

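### SAP 5.16.4 scores improvement with a strict greater-than sign, so no subject can ever be an ACR Pedi 100 responder

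*SAP*

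**What the plan says.** SAP 4.2.2 takes the endpoint definition from Protocol 2.2.3. Response at each level is "defined as $\geq 30\%$ (and 50%, 70%, 90%, 100%, respectively) improvement from baseline in at least 3 of the 6 following variables". In addition, at most one other component may deteriorate by over 30%. Improvement is therefore at-least and worsening is strictly-more-than.

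SAP 5.16.4 then gives the derivation, introduced as "Scoring algorithm including missing data handling for ACR Pedi 30, 50, 70, 90, and 100". Its text counts components "based on the number of components with worsening >30%, missing, and improvement >30% (or 50% for ACR Pedi 50, etc". The column headers of its table repeat the strict sign for improvement, but for worsening the header reads "Worsening>=30"%, whereas the sentence above the table has a strict sign. So 5.16.4 differs from 4.2.2 on improvement (text and header) and from both 4.2.2 and its own text on worsening (header).

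SAP 5.16 states that the rules in its subsections are the ones used to derive the endpoints. SAP 5.9 reports categorical efficacy endpoints as frequency, percentage and 95% CI by visit in FAS, WAS and RTAS. Section 5 asks for every analysis overall and by JIA subtype.

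**The concern.** For four of the five levels, the choice between at-least and more-than matters only for subjects exactly on the threshold. At 100% the threshold is also the largest improvement possible, so the strict sign empties the responder category.

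A programmer who follows the derivation section would produce a table showing that no child ever reached ACR Pedi 100, whatever the data. The confidence interval would make this look precise. For illustration, with 0 responders among the roughly 100 subjects expected and an exact two-sided 95% interval (the SAP does not name a method), the upper limit is 1 − 0.025^(1/100) = 3.6%. Long-term clinical benefit is a stated secondary objective, and a structural zero at the top response level would misreport it.

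At the lower levels both sign errors push the same way. Ties on improvement are scored as not improved, and ties on worsening are scored as worsened.

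**Working it through.** **Inputs**

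- Physician and patient/parent global assessments: 0 to 10 on 21 circles, so steps of 0.5 (Protocol 7.3: "disease activity for the current day by using a scale between 0 and 10 on a 21-circle VAS").
- CHAQ: mean of domain scores, each 0 to 3 (SAP 5.16.3).
- Active joints and joints with limited motion: prorated counts, minimum 0 (SAP 5.16.1 and 5.16.2).
- CRP: a concentration, which cannot be negative.
- Zero baseline (SAP 5.16.4): a rise from zero counts as worsening; otherwise "if the baseline score is 0 and the post baseline score is also zero, improvement will be set to 0"%.

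**Step 1: largest possible improvement.** For baseline b > 0 and post-baseline value p ≥ 0, improvement = 100 × (b − p)/b. This is largest at p = 0, where it equals 100 × b/b = 100% exactly. A zero baseline gives 0% or worsening. No component can therefore improve by more than 100%. Evaluating every pair on the 0.5-step global scale and on a CHAQ grid in steps of 1/8 gave a maximum of 100.0% for both.

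**Step 2: put this through the table.** Under a rule of more than 100%, the count of improved components is always 0. Every legible responder row needs at least 3. With a count of 0, the legible rows give:

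| Worsened | Missing | Outcome |
|---|---|---|
| 2 or more | any | Non-responder |
| 1 | 0, 1 or 2 | Non-responder |
| 1 | 3 or more | Missing |
| 0 | 0 or 1 | Non-responder |

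The row for no worsening and two or more missing is broken in the available text. Even if that row is read as generously as possible, a count of 0 cannot yield a responder.

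**Step 3: one worked subject.** Baseline values 6, 5, 1.5, 8, 6 and 20; all six components zero afterwards. Every improvement is 100%. The subject is a responder at 30, 50, 70 and 90 under either sign. At 100 the subject is a responder under the definition and a non-responder under 5.16.4.

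**Step 4: search for any responder.** 200,000 arbitrary profiles were generated, with each component zero at baseline with probability 0.05, zero post-baseline with probability 0.7, and missing post-baseline with probability 0.05. The worsening rule was held at more than 30%, and the ACR Pedi 100 rule was applied with each improvement sign:

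| Improvement sign | Responder | Non-responder | Missing |
|---|---|---|---|
| At least 100% | 140,063 | 38,661 | 21,276 |
| More than 100% | 0 | 199,631 | 369 |

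The zero needs no distributional assumption; the other counts depend on these inputs. The strict sign also turns most subjects who should be missing into non-responders, so the denominator changes too. Using at-least-30% for worsening while keeping the correct improvement sign reduced responders from 140,063 to 139,909, a difference of 154.

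**Step 5: ties at the other levels.** Baseline/post-baseline pairs on the 21-circle scale that meet the definition, and those exactly on the threshold, which the strict rule loses:

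| Level | Meet definition | Exact ties | Share |
|---|---|---|---|
| 30% | 158 | 2 | 1.3% |
| 50% | 120 | 10 | 8.3% |
| 70% | 74 | 2 | 2.7% |
| 90% | 32 | 2 | 6.3% |
| 100% | 20 | 20 | 100% |

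These are shares of possible pairs on one component, not of subjects.

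**The case against.** The best reply is that the endpoint itself is defined correctly. Protocol 2.2.3 and SAP 4.2.2 agree with each other, and the table headers in 5.16.4 carry the two signs in exactly reversed places, which looks like a transposition. A careful programmer might follow 4.2.2, or query a Pedi 100 rate of zero. The code is not available, and SAP 5.1 shows that at least one separate programming specification exists. Efficacy here is secondary and descriptive, with no test or comparator, and the individual components, JADAS and clinically inactive disease are reported without using this rule.

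Most of that stands. The slip is in the scoring rule, not in the definition. The zero is conditional on the rule being coded as written, and no primary or safety conclusion depends on it. It does not remove the error: SAP 5.16 makes 5.16.4 the derivation rule, the strict sign appears in both text and header, and the table prints the non-strict sign elsewhere, so a lost character in the PDF is unlikely.

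It is also fair that simulated response rates carry little weight. Under various assumed distributions, the Pedi 100 rate by the correct definition ran from about 7% to 87%. The loss was 0.4 to 7.4 percentage points at Pedi 50 and no more than 2.4 points at 30, 70 and 90. The documents do not say which scenario is realistic.

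**Conclusion.** The concern holds. As written, SAP 5.16.4 contradicts the endpoint definition in Protocol 2.2.3 and SAP 4.2.2, and it makes ACR Pedi 100 unattainable. If coded literally, there are zero responders at every visit in every analysis set and subtype. This rests only on the six components being non-negative.

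The error in the reported Pedi 100 percentage would equal the whole of the true rate, which the documents do not allow one to predict. At 30, 50, 70 and 90 the bias is always toward non-response, is confined to exact ties, and has the most tied pairs at 50. The damage is limited to the ACR Pedi summaries. It still deserves correction before any table is produced, because the written rule gives a wrong result for a named endpoint.

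**What to change.** In SAP 5.16.4:

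1. In the text, state improvement as ≥30% (≥50%, ≥70%, ≥90% and ≥100% for the higher levels).
2. In the table, change the improvement header to ≥30%, with the same substitution by level.
3. In the table, change the worsening header to >30%, matching the text above it and SAP 4.2.2.

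The endpoint definition needs no change. Check the derivation code with two kinds of test record: one with all six components at zero post-baseline, and one lying exactly on each improvement threshold and on 30% worsening. SAP 2.2.2 plans descriptive analyses at least every two years, so confirm which rule any earlier ACR Pedi tables used and rerun them if it was the strict one. The cost is three symbols and a short code check, with no effect on data collection or study conduct.
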